15.2 Qualitative data

To determine the feasibility, acceptability and safety of the intervention interviews will be analysed using the five iteratives stage of the Framework Analysis method (familiarisation, thematic framework identification, indexing, charting, mapping and interpretation) [30]. This method incorporates both deductive and inductive coding and provides a strong audit trail of the analytical process from original transcripts to final themes, including illustrative quotes [31], and enables trial processes and positive as well as negative participant experiences to be explored and reported. Deductive trial factors will include factors relating to feasibility, acceptability and adoption of technology which will be informed by the theoretical framework of acceptability [32] and the NASSS Framework [33].

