4. STUDY DESIGN

Using SCS we aim to examine the effect of FES applied to the quadriceps muscles for 2-4 hours a day, 6 days a week, over an 8-week period in children with CP who have a crouch gait. The FES application and stimulation parameters will follow previous work [16].

The effects of FES will be investigated using an AB single case study design. There will be an initial 8-week baseline period over which serial outcome measures (walking, muscle strength and perceived walking ability and fatigue) will be taken (figure 1). The FES will be issued in week 9 with a one-week period to determine the optimal simulation parameters. There will then be 8 weekly assessments while the FES being used (week 10-18). There will be a final assessment at week 20 where a semi-structured interview will occur (figure 1). At the start and end of each phase (weeks 1, 8, 10, 19) there will be a more in-depth assessment of impairment (muscle strength, passive range of motion and selective motor control).

The research question can be framed as follows:

Population: Ambulatory Children with bilateral Cerebral Palsy, age 8-18 years old, GMFCS level I-III

Intervention: Functional Electrical Stimulation applied to the quadriceps during stance phase of gait or Tibialis anterior during the swing phase of gait for 2-4 hours a day, 6 days a week

Time: 8 weeks FES intervention

Outcome:

[figure not shown]
Primary: The effect of FES on knee flexion angle during mobility tasks (walking on the flat and up/downstairs), as measured by an electric goniometer at initial contact and midstance.

Secondary: Effect of FES on:

- Muscle strength, passive range of motion, selective motor control.
- Parents' perception of gait and child's perception of fatigue and gait
- Acceptability of FES as an intervention for crouch gait using semi structured interviews with parents and children/young people.

Health Research Authority

Figure 1. Study timeline diagram

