11 QUALITATIVE EVALUATIONS

11.1 CYP and Parent Interviews

Interviews will be conducted in person or over video call at the end of FES intervention (week 20) (see figure 1). In person interviews will be in the CYP home with their permission. The interviews will be conducted by the SC following topic guides developed from the TFA. Each interview will last approximately 45 minutes and will follow the interview schedule outlined in Appendix 5.

[figure not shown]
12.RECRUITMENT

Recruitment will take place simultaneously across each Child Development Centres (CDCs) and Community Paediatric Outpatient physiotherapy services. These include Plymouth Hospitals NHS Trust, Torbay and South Devon NHS Trust, Royal Cornwall Hospitals NHS Trust and Royal Devon and Exeter NHS Trust. The study will be advertised via interest groups, University of Plymouth website and charity / support group websites (e.g Cerebra). In preparation for recruitment, the SC will visit each site to familiarise physiotherapists with the eligibility criteria and study procedures.

Potential study participants will be identified, screened, and recruited as shown in Figure 9.

Figure 9. Diagram of recruitment

- Recruitment will take place simultaneously in each NHS trust, the university of Plymouth and via social media
- In preparation for recruitment the SC will visit each recruiting sites to familiarise recruiting clinicians with eligibility and study procedure.
- Once a child has been recruited and identified as a suitable candidate to
 participate in the study the SC will contact their parents to arrange an
 appointment for them attend the study assessment at the University of
 Plymouth.

Health Research Authority

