17. ADVERSE EVENTS

17.1 Recording and reporting of AEs

An adverse event (AE) is defined as any unfavourable and unintended sign that develops or worsens during the period of the trial, whether or not it is considered to be related to the trial. The risks of taking part in this trial have been assessed to be low.

Any new or worsening problems, which participants perceive to be related to participation in the study and occur at the single visit and within the following 48 hrs will be captured.

Examples of AEs that require reporting include:

- Aches and pains in the leg muscles following FES stimulation, lasting over 1 hour following cessation of the stimulation or requiring pain relief
- Fatigue following FES intervention lasting more than 1 day
- · Injury related to the study procedure or data collection
- Red marks or a reaction on the surface of the skin because of contact with FES electrode pads, which last for more than 10 minutes after data collection is complete.

Participant's parent and or guardian will be asked to report any AE's that occur for the duration of the study to the Cl/ SC. These will be gathered during the weekly face-to-face measurement sessions. Recorded AEs and SAEs will be presented at a

Health Research Authority

Study management Group (SMG) meeting for review. The SMG will refer concerns to the Study Steering committee (SSC) for further review if required. AEs considered related to study participation will be followed until resolution or the event is considered stable. If the AE occurs during the study assessment the Study Coordinator (SC) in discussion with the participant parents/Guardian will take responsibility as to whether an AE is of sufficient severity to withdraw the participant from the study. The participant may also voluntarily stop participating in the study if he or she perceives an incident to be an intolerable AE.

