21.4 Appendix 4 - Interview Schedule

Torbay Medical Research Fund

V1: 17/07/2024

FES in CP: Interview schedule

Questions will not necessarily be asked in this order nor phrased in the way presented here.

Consent

- Discuss purposes of the interview:
 - to find out you and your parents view on the FES study, how it went for you, whether you or your parent think it made any difference, and how we can improve it.
 - o To learn what you thought about taking part in the research study.
- So it is important to be as honest as you can so we know what works and what needs to change. You don't have to answer any question, and can stop whenever you want
- I'll record the interview so I can listen to you properly. What you say will remain confidential to the research team. Anything you say about the study will be anonymised to protect your identity.
- Any time limitations or other issues with being interviewed now? It may last up to about an hour and a half.
- Obtain written consent.

Overview of condition

- Briefly, when you started the study what issues did you face when walking?
 - Prompts: tiredness, difficulties walking far, walking more slowly than your friends, tripping/difficulty walking on uneven surfaces/difficulties up and down slopes and stairs
- How have these changed over the last 8 weeks? Has anything about your walking improved or got worse?
- Were any other illnesses/conditions an issue for you in the last 8 weeks?

Preparing to take part in FES in CP study

- Why did you want to take part in this study?
 - o What were you hoping for from taking part in the FES study?
 - o Prompts: goals
- Did you know enough about what was involved in the study before you took part?
- Did you have any concerns about taking part? If so, what were these?

Preparation for Intervention

- At the start of the study your received training on with FES. How did you find the training?
 - o Prompts:
 - What did you find helpful / unhelpful in the way you were trained?
 - How well did they take account of your own needs/ circumstances (therapeutic alliance, fatigue)
 - At the end did you have enough knowledge to use FES?
 - How confident did you feel to use the FES?
- What did you understand the purpose of the FES to be?

Questions regarding the FES (bring device used as visual prompt)

- How able were you to put on and use the device by yourself?
 - o If no, what aspects did you need help with?
- What would make it easier to put it on?

Using the FES

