In your own words can you tell me about your experience of using FES as part of this study?

Prompt questions

- o How did you feel using the FES?
- Did your feelings about using the FES change from the beginning of the study to the end?
- o Was there anything you liked / disliked about the FES?
- o How much effort did you have to make to use FES?
- o How did you find recording your daily use in the diary?
- Did you suffer from any problems/adverse effects while using the FES (Skin soreness/muscle aches and pains/tiredness?)
 - If anything, that can we change to prevent these from happening?
- How did you find putting on and off the electrodes and caring for the electrodes?
- o Do you think the FES has had any impact on your walking?
- Do you think using the FES for 8 weeks had any effect on your leg or walking ability? If so, can you describe the main effect you felt it had?
- o Was there anything that put you off using FES?
- o If the opportunity arose would you want to keep the FES? Why?

External Support

Commented [[name]]: No diary now just FES stepp and duration tracker

- During the study did you receive support from anyone/where else with using the FES?

Prompts:

- Friends or family
- Physiotherapist/private therapist
- And what support did they give you with using the FES?
- What did you think about the technical support offered? Was it adequate/lacking?

General question inpatient and home use

How did it using the FES compare to your usual physiotherapy routine? (tiredness enjoyment, time taken)

Taking part in the research

Questions regarding the study:

How did you find the assessment and researchers taking different measurements?

- Meeting with the assessor
- Performing the different assessments
- How did you find the research team ([name])?
- Is there anything we could have done differently to make it a better experience for you?
- Would you be willing for us to contact you again in the future about this study or other studies related to CP?
- Would you like to receive a report of this study?
- Is there anything else you would like to say about FES or this study?

Conclusion

Thank them for their time.

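### Section 15.2 assigns the safety conclusion to a single week-20 interview, which on the stated schedule does not reach a child who withdraws earlier, and section 15 does not link the weekly adverse event record to it

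*Protocol*

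**What the plan says.** Section 15.2 of the protocol, on qualitative data, opens: "To determine the feasibility, acceptability and safety of the intervention interviews will be analysed", by the stages of Framework Analysis. It then lists what the coding will look for: "Deductive trial factors will include factors relating to feasibility, acceptability and adoption of technology". Safety is not in that list.

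On timing, section 4 says "There will be a final assessment at week 20 where a semi-structured interview will occur", and section 11.1 says "Interviews will be conducted in person or over video call at the end of FES intervention (week 20"). No other interview is described.

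Adverse events are handled in section 17. Section 17.1 asks parents or guardians to report them and says "These will be gathered during the weekly face-to-face measurement sessions". The management group reviews them and can refer concerns to the steering committee. Section 17.3 has them verified and entered on the study database. Section 12.6 keeps a withdrawn child's data up to that point for analysis, unless the family asks for its destruction.

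**The concern.** Section 15.2 is a positive statement of which data determine safety, so this is more than a detail left for a statistical analysis plan. The named source has two weaknesses.

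- **Selection.** Whether a child is interviewed depends on staying to week 20, and the protocol itself names harm as a reason for leaving. Section 10.1 accepts that a child who cannot tolerate the sensation at set-up may withdraw. Section 17.1 provides for withdrawal because of an adverse event. The missing interviews are therefore related to the outcome.
- **Recall.** The examples of reportable events in section 17.1 are brief, and the interview asks about them weeks later.

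Both weaknesses push a safety statement towards reporting few problems. The study is meant to inform a randomised trial (section 2), so an optimistic account of tolerability would carry forward.

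**Working it through.** The plan gives no safety figure to reproduce. The check sets the sections side by side, with simple arithmetic.

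**1. Who is covered**

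| Source | Timing | Child who withdraws at week 9 because of intolerance |
|---|---|---|
| Interviews (4, 11.1) | Once, week 20 | No interview described |
| Adverse event record (17.1, 17.3, 12.6) | Weekly sessions, entered on the database | Data kept up to withdrawal, unless destruction is requested |

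The planned sample is 12 (section 15.3). The protocol gives no dropout rate, so the number of withdrawals w before week 20 is my assumption. Interview coverage = (12 − w)/12:

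- w = 1: 11/12 = 92%
- w = 2: 10/12 = 83%
- w = 3: 9/12 = 75%

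To show the direction of the bias, suppose one child withdraws at set-up because of a device-related harm and no other child has one. A complete adverse event record shows 1 of 12 children affected (8.3%). The interviews show 0 of 11.

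**2. Length of recall**

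First exposure is at set-up in week 9 (section 10.1) and the interview is in week 20. Recall = 20 − 9 = 11 weeks. A weekly enquiry looks back about 1 week. The examples in section 17.1 include skin marks lasting over 10 minutes, muscle aches over 1 hour and fatigue over 1 day.

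**3. Whether another sentence names a better source**

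Section 15.1 covers the serial measures and the four in-depth assessments. Section 15.2 covers the interviews. Neither mentions adverse events. The objectives (section 3) and outcome lists (13.2, 13.3) contain no safety objective and no adverse event outcome. The opening of section 15.2 is therefore the only statement of how a safety conclusion is to be reached.

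**4. Whether the section 17 record can take its place as written**

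Section 17.1 gives two capture windows. One covers problems at a single visit and in the 48 hours after it. The other asks for reports over the whole study. If the first were applied to each weekly visit, it would cover 48 of 168 hours, or 29% of the week, while section 10.4 asks for device use on 6 days a week. The two statements must be reconciled before the record can be called complete.

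**The case against.** **Safety data are not ignored.** Adverse events are gathered weekly, reviewed and put on the database, and data up to withdrawal are kept. A reader might infer from section 15.2 that the weekly record is excluded from the safety conclusion, or that a child who withdraws contributes nothing to it. The documents support neither reading. Section 15.2 does not say that interviews are the only source, and an adverse event table may sit in a statistical analysis plan that is not shown. Its absence from section 15 would be no finding on its own. What stands is that the one sentence assigning the determination of safety assigns it to the interviews.

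**Early harms are not missing for interviewed children.** One might infer from "Were any other illnesses/conditions an issue for you in the last 8 weeks" that at week 20 the interview reaches back only to week 12 (20 − 8), and so misses the first three weeks after set-up in week 9. That question concerns other illnesses. The adverse effects prompt in Appendix 4 asks about problems "while using the FES (Skin soreness/muscle aches and pains/tiredness"), with no 8-week limit. For interviewed children, early harms are subject to recall; they are not left out.

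**The interviewer is not a separate argument.** The study co-ordinator sets up the device and conducts the interview, but also holds the weekly sessions and checks for adverse events. Changing the source does not change the collector.

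**Framework Analysis yields themes, not rates.** This is correct. The percentages above describe which children are heard, not an event rate.

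**Conclusion.** The concern holds in a limited form. Section 15.2 names an unsuitable source for the safety conclusion: one interview at week 20 that relies on up to 11 weeks of recall and, as scheduled, does not reach a child who withdraws earlier. Each such child is 1 of 12 (8.3%) of the planned sample. The actual loss depends on a withdrawal rate that the protocol does not state. If every child reaches week 20, only the recall problem remains.

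This rests on two readings: that section 15.2 means what it says about safety, and that no interview is held at withdrawal because none is described. It does not show that harms will go unrecorded. The protocol already sets up a prospective record that section 15 could use, once its capture window is settled. The correction should be made before analysis begins.

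**What to change.** 1. In section 15.2, delete safety from what the interviews determine, leaving feasibility and acceptability.
2. In section 15, state that safety is determined from the section 17 adverse event and serious adverse event record for every child issued a device, withdrawals included. Report the number of children affected and the number of events, with logged duration of FES use (section 9.2.3) as context. Interviews serve as explanatory data only.
3. In section 17.1, reconcile the two capture windows so that the record has one stated period.
4. In section 11.1, offer the planned interview to children who stop early, at the time they stop.

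The cost is wording and one small table from data already being collected. The small downside of item 4 is an occasional interview before week 20, and the family may decline it.

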15.3 Sample size calculation

As a single case design, no formal sample size has been calculated through statistical analysis. The total sample size of 12 has been estimated based on the length of the study design, access to measurement and intervention resources and the set time frame of 15 months to complete the study. Each single case study lasts for 20 week (4.5 months). There are x4 FES units available at any one time. We intend to recruit x2-4 people / month. Therefore, we should be able to recruit to target within 15 months.

16.SAFETY AND MANAGEMENT OF RISK

Health Research Authority

16.2. Clinical measures

The SC has training and experience from a previous observational study in carrying out the SCALE, PROM and MTS, MTS using a goniometer, Hand Held Dynamometer and in using the electrogoniometers. The participant will also be given a verbal explanation of what will happen during the clinical measures, and they will have the opportunity to stop the assessment at any time. For the clinical measures the participant will position themselves in sitting or lying in accordance to what is required for the assessment. This will be on a height adjustable plinth if taking place in a clinic setting or at home on a bed if. If taking place on a plinth the CI and SC to raise the plinth to a suitable height during the assessment, thus reducing manual handling risks. If taking place at home the SC will need to be mindful of their own posture and position when carrying out assessments and make adjustments as required to minimise any manual handling risks. If a participant has difficult moving themselves from lying to sitting or transferring onto a plinth or bed, they will be assisted by the CI and SC using appropriate risk assessed, manual handling techniques. The CI and SC will have up to date manual handling qualifications and training in place.

CYP will be accompanied during the walking and stairs measures to prevent and reduce the risk of falls. The stairs will either be the ones situated in their own home, which they are familiar with, or ones situated within the university or clinic setting with handrails.

16.3 Loan working in the community setting

CYP and parents will have the choice to be seen at home for their baseline and weekly assessments or within a clinic or university lab setting. The site chosen will remain the same for the CYP for the study duration. If CYP selects the community setting, which could be either the CYP home or local clinic, the SC will inform the CI of the date and time of each appointment as well as the CYP home address. The SC will also telephone or text the CI at the end of the appointment to inform them that they are safe. The SC will have their mobile phone on them with them for the

duration of the study appointment so If they feel unsafe during a home visit they can make contact with the CI or the emergency services.

16.4 RISK Level

A risk assessment has been completed, (please refer to the Risk assessment document). This suggest that the study is of 'Low Risk' category and the appropriate steps will be taken to mitigate any potential risks posed to participants and no further action is required.

17. ADVERSE EVENTS

17.1 Recording and reporting of AEs

An adverse event (AE) is defined as any unfavourable and unintended sign that develops or worsens during the period of the trial, whether or not it is considered to be related to the trial. The risks of taking part in this trial have been assessed to be low.

Any new or worsening problems, which participants perceive to be related to participation in the study and occur at the single visit and within the following 48 hrs will be captured.

Examples of AEs that require reporting include:

- Aches and pains in the leg muscles following FES stimulation, lasting over 1 hour following cessation of the stimulation or requiring pain relief
- Fatigue following FES intervention lasting more than 1 day
- · Injury related to the study procedure or data collection
- Red marks or a reaction on the surface of the skin because of contact with FES electrode pads, which last for more than 10 minutes after data collection is complete.

Participant's parent and or guardian will be asked to report any AE's that occur for the duration of the study to the Cl/ SC. These will be gathered during the weekly face-to-face measurement sessions. Recorded AEs and SAEs will be presented at a

Health Research Authority

Study management Group (SMG) meeting for review. The SMG will refer concerns to the Study Steering committee (SSC) for further review if required. AEs considered related to study participation will be followed until resolution or the event is considered stable. If the AE occurs during the study assessment the Study Coordinator (SC) in discussion with the participant parents/Guardian will take responsibility as to whether an AE is of sufficient severity to withdraw the participant from the study. The participant may also voluntarily stop participating in the study if he or she perceives an incident to be an intolerable AE.

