10.2 Intervention Training

The CYP and their parent will receive training on using their FES device. General training will include donning and doffing of the FES device, use of the FES, care of the electrode, electrode placement and potential adverse skin reactions to electrode pads. All of this will be documented in an information leaflet (see Appendix 4) for them to take home with their FES device. Participants will be taught how to monitor possible training effects of FES such as; transient muscle fatigue, and post exercise muscle soreness, which are normal physiological responses to walking practise whilst wearing FES.

[figure not shown]

Figure 8. A Placement of foot switch in the heel of cork insole. B Placement of the foot switch on the 1st metatarsal head

Once FES training is complete the CYP will be issued with the FES devices and bag of accessories to take home.

- FES device and battery
- FES set of electrode wires and foot switch wire
- 1 Set of Electrodes
- · Airtight bag to store electrodes.
- User Instruction Manual
- Cork Insole and foot switch
- FES pouch, to hold FES device when wearing it.
- FES supporting leaflets.

Health Research Authority

Following FES training the CYP will be asked to use the FES daily, this should start in and around the house, but building up confidence to wearing it in the community setting or at school. The aim is to build up over 1 week to wearing the FES for between 2-4hours a day in preparation for starting the FES intervention phase of the study at week 11. One week after receiving FES training (Week 10), the participant will receive a home visit from the physiotherapist to check the CYP has been using it correctly and to make any changes required to optimise gait.

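### Section 17.1 defines adverse events regardless of cause, but its capture sentence depends on perceived relatedness and conflicts with its own whole-study weekly reporting rule

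*Protocol*

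**What the plan says.** Protocol section 17.1 contains three statements about what counts as an AE and what is recorded.

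- **Definition.** An AE is "any unfavourable and unintended sign that develops or worsens during the period of the trial, whether or not it is considered to be related".
- **Capture sentence.** The next paragraph says that what is recorded is "Any new or worsening problems, which participants perceive to be related to participation in the study", and that these "occur at the single visit and within the following 48 hrs will be captured".
- **Weekly rule.** Further down, parents or guardians are to be asked for any AE over the whole study, and the reports are gathered at the weekly face-to-face sessions.

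The section also lists example events that must be reported. One is "Aches and pains in the leg muscles following FES stimulation, lasting over 1 hour following cessation of the stimulation or requiring pain relief". Another is fatigue after FES that lasts more than 1 day.

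Section 17.3 makes the study co-ordinator responsible for checking for AEs when a participant attends. It requires a causality assessment on the form for serious adverse events (SAEs).

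Section 10.2 covers training: "Participants will be taught how to monitor possible training effects of FES such as; transient muscle fatigue, and post exercise muscle soreness". It then describes them as effects "which are normal physiological responses to walking practise whilst wearing FES". It does not mention the 1-hour, pain-relief or 1-day limits of 17.1.

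**The concern.** A definition that ignores cause and a capture sentence that depends on perceived cause cannot both govern the AE record. Under the capture sentence, attribution is made by the child or family before anything is written down, so an event they attribute to cerebral palsy is never available for the investigator to assess and judge unrelated. Under the weekly rule, the same event is recorded.

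The series is meant to inform a randomised trial (section 2), and section 15.2 includes safety among its aims. With 12 children, one or two events recorded or not would visibly change the picture of tolerability. The co-ordinator could follow either sentence and be compliant, so the record may not be collected in the same way across children or across weeks.

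**Working it through.** The protocol states no AE rate or expected count, so there is no figure to reproduce. The check sets the rules side by side.

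| Feature | Definition (17.1) | Capture sentence (17.1) | Weekly rule (17.1) |
|---|---|---|---|
| Relatedness | Irrelevant | Perceived by the participant | Not a condition |
| Period | Whole trial | One visit plus 48 hours | Whole study |
| Who decides or reports | Not stated | Participant | Parent or guardian |

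**Step 1: relatedness.** Take a fall at home in week 13 that the family attributes to cerebral palsy. It meets the definition and falls under the weekly rule. It does not meet the capture sentence. The three statements give two different answers for one event.

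**Step 2: time window.** The same capture sentence limits the period. One week is 7 × 24 = 168 hours.
- If the 48 hours are counted after each weekly visit, coverage is 48/168 = 0.286, or about 29% of the week, while FES is to be used 6 days a week.
- If the text is read literally as one visit in a 20-week study, coverage is 48/(20 × 168) = 48/3,360 = 0.014, or about 1.4%.
- Under the weekly rule, coverage is 100%.

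These are shares of calendar time (the visit itself is ignored), not estimates of missed events.

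**Step 3: does the rest of the safety section settle which rule applies?** It does not.
- The four example events are all tied to the study by their wording: two follow stimulation or the FES intervention, one is injury related to study procedures, and one is a skin reaction caused by the electrodes. None is an event that a family might attribute to the underlying condition.
- The duty to check in 17.3 does not say which definition the check uses.
- Nobody is named to judge relatedness of a non-serious AE, although 17.1 follows to resolution those considered related.

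**Step 4: section 10.2 against 17.1.** Section 10.2 concerns transient effects. Section 17.1 makes aches reportable beyond 1 hour or when pain relief is needed, and fatigue beyond 1 day. Brief effects can be expected and longer ones reportable, so the two sections are compatible. What is missing is a pointer in 10.2 showing where expected ends and reportable begins.

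**The case against.** The strongest reply is that capture is not restricted to what families perceive as related. The weekly rule in 17.1 carries no such condition, and 17.3 adds a duty to check. That is correct: a reader might infer from the capture sentence that only perceived-related problems are recorded, but the section does not support it. The defect is a conflict between rules.

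A reader might also infer that families are taught to disregard soreness and fatigue, so that the main expected harms will be under-reported. The text does not support this either.
- Section 10.2 tells families to monitor these effects and presents them as effects of FES. A family told this is, if anything, more likely to see them as study-related. Normal does not mean unrelated.
- Skin reactions are described in 10.2 as adverse, so the point does not extend to them.
- The leaflets that document the training were not in the text available for this review and may state the limits.

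Other data would show part of what the AE record might miss. Fatigue and walking ability are self-reported weekly (9.2), gait is measured weekly (9.1.4), the GOAL questionnaire has a pain, discomfort and fatigue domain (7.3.4), and the week-20 interview asks about skin soreness, aches and tiredness (Appendix 4). Any emergency department attendance counts as an SAE under 17.2 whatever its cause. These sources lower the risk that such harms go wholly unseen. However, nothing stated routes the questionnaire or interview answers into the AE record, and a fall without hospital contact has no other stated route. The conflict in 17.1 therefore stands.

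**Conclusion.** Section 17.1 contradicts itself on which AEs are recorded. The capture sentence departs from the section's own definition ("whether or not it is considered to be related to the trial") and from its weekly rule, in both relatedness and period. If the capture sentence is applied, events that meet the definition may go unrecorded, chiefly those that families attribute to cerebral palsy. The missing cross-reference in 10.2 is secondary and depends on leaflets that could not be seen.

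The extent of under-recording cannot be computed from the protocol. Any proportion would be the product of an assumed event rate and an assumed reporting rate, neither of which the protocol gives. The conclusion therefore goes no further than that AEs may be under-recorded and that counts will depend on which sentence is followed. The correction is worth making because it removes an avoidable source of bias from the safety record for very little effort.

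**What to change.** In section 17.1:
- Delete the clause that makes capture depend on what participants perceive as related.
- In the same sentence, reconcile the reference to one visit and 48 hours with the whole-study weekly rule.
- State that all new or worsening problems are recorded at the existing weekly visits, whatever the family believes the cause to be, and that the investigator assigns relatedness after recording.

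In section 10.2, add a cross-reference to the reporting limits already stated in 17.1, and check that the leaflets agree. No limit needs to change. A fixed set of weekly AE questions would help consistency but is optional; the contradiction can be resolved without it.

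The cost is a few wording changes, with no new visits or staff. The downside is that more minor and unrelated AEs will be on record, each needing a relatedness judgement.
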